8.7 Data Management and Analysis

Case report forms will be created for management of data collected during this study, and will be available in electronic format. A database in Access will be created based on the case report forms. All study data will be imported into SAS and data management will be utilized to flag, and generate queries on out of range data issues until they are resolved. All analysis will be performed using SAS software version 9.4 (SAS Institute Inc. Cary, NC).

Amendment9 09NOV2021 Page 43 of 77

9.0 SAFETY REPORTING

9.1 Definitions

9.1.1 Adverse Event Definition

An adverse event (AE) is any new untoward medical occurrence or worsening of a preexisting medical condition in a patient administered a pharmaceutical product, which does not necessarily have a causal relationship with the treatment. An adverse event can be any unfavorable and unintended sign (e.g., including an abnormal laboratory finding), symptom, or disease temporally associated with the use of the drug, whether or not it is considered to be drug related. This includes any newly occurring event or previous condition that has increased in severity or frequency since the administration of drug. The following information should be considered when determining whether or not to record a test result, medical condition, or other incident when collecting and reporting Adverse Events:

- From the time of informed consent through the day prior to Day 1 Week 1 of combined checkpoint therapy, only study protocol-related AEs should be recorded. A protocolrelated AE is defined as an untoward medical occurrence as a result of a protocol mandated procedure that is not standard of care.
- All medical conditions present or ongoing pre-dose on Day 1 Week 1 of combined checkpoint therapy should be recorded.
- All AEs or complications associated with any procedures (study related or not) should be recorded from Day 1 Week 1 of combined checkpoint therapy through the end of the safety-reporting period of 100 days after the last dose of study therapy or until the start of a subsequent systemic anti-cancer therapy, if earlier.
- Changes in medical conditions and AEs, including changes in severity, frequency, or character, during the safety-reporting period should be recorded.
- Generally, abnormal laboratory values should not be recorded as an AE unless it is
 associated with clinical signs or symptoms requires an intervention, or results in a serious
 adverse event, or results in study termination, or interruption/discontinuation of study
 treatment. When recording an AE resulting from a laboratory abnormality, the resulting
 medical condition rather than the abnormality itself should be recorded.

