5.7 Dose Delay Criteria

Dose delay criteria apply for all drug-related adverse events (regardless of whether or not the event is attributed to nivolumab, ipilimumab or both). All study drugs must be delayed until treatment can resume. In the case that a treatment cannot be administered at a scheduled visit (with +/-2 day window), proceed to the next scheduled dose.

Nivolumab and ipilimumab administration should be delayed for the following:

• Any Grade ≥ 2 non-skin, drug-related adverse event, with the following exceptions:

- Grade 2 drug-related fatigue or laboratory abnormalities do not require a treatment delay
- Any Grade 3 skin, drug-related adverse event
- Any Grade 3 drug-related laboratory abnormality, with the following exceptions for asymptomatic amylase or lipase, AST, ALT, or total bilirubin:
 - Grade 3 amylase or lipase abnormalities that are not associated with symptoms or clinical manifestations of pancreatitis do not require a dose delay. It is recommended to consult with the principle investigator for Grade 3 amylase or lipase abnormalities.
 - If a subject has a baseline AST, ALT, or total bilirubin that is within normal limits, delay dosing for drug-related Grade ≥ 2 toxicity
 - If a subject has baseline AST, ALT, or total bilirubin within the Grade 1 toxicity range, delay dosing for drug-related Grade ≥ 3 toxicity
- Any adverse event, laboratory abnormality, or intercurrent illness which, in the judgment of the investigator, warrants delaying the dose of study medication.

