5.9 Discontinuation Criteria

Treatment should be permanently discontinued for the following:

 Any Grade 2 drug-related uveitis or eye pain or blurred vision that does not respond to topical therapy and does not improve to Grade 1 severity within the re-treatment period OR requires systemic treatment

Amendment9 09NOV2021 Page 30 of 77

- Any Grade 3 non-skin, drug-related adverse event lasting > 7 days, with the following exceptions for drug-related laboratory abnormalities, uveitis, pneumonitis, bronchospasm, diarrhea, colitis, neurologic adverse event, hypersensitivity reactions, and infusion reactions
 - Grade 3 drug-related uveitis, pneumonitis, bronchospasm, diarrhea, colitis, neurologic adverse event, hypersensitivity reaction, or infusion reaction of any duration requires discontinuation
 - Grade 3 drug-related laboratory abnormalities do not require treatment discontinuation except those noted below
 - Grade 3 drug-related thrombocytopenia > 7 days or associated with bleeding requires discontinuation
 - Any drug-related liver function test (LFT) abnormality that meets the following criteria require discontinuation:
 - AST or ALT > 8 x ULN
 - Total bilirubin > 5 x ULN
 - Concurrent AST or ALT > 3 x ULN and total bilirubin > 2 x ULN
- Any Grade 4 drug-related adverse event or non-hematological laboratory abnormality, except for the following events which do not require discontinuation:
 - o Isolated Grade 4 amylase or lipase abnormalities that are not associated with symptoms or clinical manifestations of pancreatitis and decrease to < Grade 4 within 1 week of onset.
 - Isolated Grade 4 electrolyte imbalances/abnormalities that are not associated with clinical sequelae and are corrected with supplementation/appropriate management within 72 hours of their onset
- Any dosing interruption lasting > 6 weeks with the following exceptions:
 - Dosing interruptions to allow for prolonged steroid tapers to manage drug-related adverse events are allowed. Prior to re-initiating treatment in a subject with a dosing interruption lasting > 6 weeks, the Investigator must be consulted. Tumor assessments should continue as per protocol even if dosing is interrupted

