8.2 Populations for Analysis

- The All-Subjects-as-Treated (ASaT) population will be employed for safety analyses. Descriptive tables that summarize the number and percentage of subjects that experience adverse events as categorized in the NCI CTCAE Version 4.03 will be generated by cohort/group.
- The intent-to-treat (ITT) population will be employed for response and PFS analyses.
 Descriptive tables that summarize the number and percentage of subjects with responses and PFS will be generated by cohort/group.

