8.4 Additional Endpoint Analyses

8.4.1 Toxicities of the treatments

The toxicity of combined checkpoint inhibition with nivolumab and ipilimumab after autologous hematopoietic stem cell transplantation in patients at high risk for post-transplant recurrence will be evaluated for all adverse events with grade 3 or grade 4 observed in each cohort and presented as counts (proportion) and corresponding exact binomial 95% confidence intervals for proportion.

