8.4.3 General Data Analysis

The summary of the demographic characteristics will be presented. Continuous variables will be summarized using mean (SD) or median (interquartile range) depending on whether or not the data follow the normal distribution. Categorical variables will be summarized by frequency (percentage). All adverse events will be presented as listings. All analysis will be performed using SAS version 9.4 (SAS Institute Inc. Cary, NC, USA).

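### Minor, cheap improvement: the grade 3–4 toxicity summary counts recorded adverse events only, so asymptomatic grade 3 lipase or amylase can stay out of every planned safety table

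*Combined protocol and SAP*

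**What the plan says.** **Recording.** The laboratory rule in 9.1.1 begins "Generally, abnormal laboratory values should not be recorded as an AE unless it is". It then lists what makes a value recordable: signs or symptoms, a need for intervention, a serious adverse event, study termination, or interruption or discontinuation of study treatment. When the rule is met, the resulting condition is recorded rather than the laboratory value. Collection runs through a "safety-reporting period of 100 days after the last dose of study therapy", or to the next systemic anti-cancer therapy if that comes first.

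**Dosing rules that trigger recording.** Section 5.7 opens with "Dose delay criteria apply for all drug-related adverse events". It requires a delay for drug-related grade 3 laboratory abnormalities, with exceptions. One is that "Grade 3 amylase or lipase abnormalities that are not associated with symptoms or clinical manifestations of pancreatitis do not require a dose delay". Section 5.9 adds that "Grade 3 drug-related laboratory abnormalities do not require treatment discontinuation except those noted below"; those noted are thrombocytopenia that lasts or bleeds, and liver function tests beyond set multiples of the upper limit.

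**Analysis.** Section 8.2 plans "Descriptive tables that summarize the number and percentage of subjects that experience adverse events as categorized in the NCI CTCAE Version 4.03". Under 8.4.1, toxicity "will be evaluated for all adverse events with grade 3 or grade 4 observed in each cohort", with counts, proportions and exact binomial 95% intervals. Section 8.4.3 says "All adverse events will be presented as listings". None of these plans a worst-grade table, shift table or listing of laboratory values. Within section 8, laboratory abnormalities are named in the Phase IIA definition of unacceptable toxicity in 8.6.

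**The concern.** Determining the toxicities of the treatment is a secondary objective in both phases, and the grade 3–4 rate per cohort in 8.4.1 is its main summary. If a grade 3 laboratory value never becomes an adverse event, that rate omits it and no other planned output shows it.

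The omitted category matters for this drug pair. Section 2.2 describes the combination in advanced melanoma and gives lipase (13%), AST (13%) and ALT (11%) as the most common grade 3–4 treatment-related events. It also says that nivolumab 3 mg/kg with ipilimumab 3 mg/kg exceeded the maximum tolerated dose because three of six patients had persistent asymptomatic grade 3–4 lipase elevation. That dose is not used here, so the finding does not carry over as a rate. It does show that silent lipase elevation has informed dose decisions. A reader comparing this trial's grade 3–4 rate with such reports could not tell whether laboratory events were counted in the same way.

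**Working it through.** There is no plan figure to reproduce. The check follows each kind of grade 3–4 laboratory value through the recording rules, then illustrates size.

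**Which values reach the record**

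| Laboratory value | Route into the adverse event record | Result |
|---|---|---|
| Drug-related grade 3 neutropenia or thrombocytopenia, on treatment | 5.7 delay, which meets the 9.1.1 interruption condition | Recorded |
| Drug-related AST, ALT or bilirubin | 5.7 delay at grade 2 or above (normal baseline) or grade 3 or above (grade 1 baseline); Appendix E also lists transaminase elevations | Recorded |
| Creatinine elevation; grade 4 anemia | Listed as events of clinical interest in Appendix E | Separate reporting route |
| Laboratory values meeting 5.9, on treatment | Discontinuation, which meets the 9.1.1 condition | Recorded |
| Asymptomatic grade 3 lipase or amylase | Exempt from delay in 5.7, no discontinuation under 5.9, lipase and amylase not listed in Appendix E | No required route |
| Values first found after the last dose, without symptoms or intervention | No dose left to interrupt | May be missed, apart from Appendix E items |

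The last row is a real possibility: Appendix D schedules lipase and amylase at the end-of-treatment visit, and blood counts and chemistry then and at later visits.

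**Illustration of size**

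Inputs from the melanoma study in 2.2: 53 patients at pooled doses, 13% with grade 3–4 lipase elevation, 53% with any grade 3–4 treatment-related event. Cohort sizes are 7 (Phase Ib) and 37 (Phase IIA), from 8.1.

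- No overlap with other grade 3–4 events: 0.13 × 7 = 0.91 patients; 0.13 × 37 = 4.81 patients.
- Full overlap: 0 patients added.
- Independence (an assumption): the share of lipase patients with no other event is (1 − 0.53)/(1 − 0.13) = 0.47/0.87 = 0.540. Then 0.13 × 0.540 = 0.070, or 7.0 points: 0.49 of 7 patients, 2.60 of 37.

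These figures precede removal of symptomatic, held or otherwise recorded cases. They also include the group above the maximum tolerated dose. Taking 13% of 53 as 7 patients (0.13 × 53 = 6.89), and assuming that the three affected patients of that group of six are among them, leaves (7 − 3)/(53 − 6) = 4/47 = 8.5% at the other doses. The illustration covers lipase only; the documents give no basis for sizing the last row of the table.

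**Against sampling error.** One missed patient moves a cohort's rate by 1/7 = 14.3 points or 1/37 = 2.7 points. The exact 95% interval for 1/7 is 0.4% to 57.9%, a half-width of about 29 points. For an assumed 9/37 (24.3%) it is 11.8% to 41.2%, a half-width of about 15 points. The shift from one patient is well inside both.

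**The case against.** The strongest reply is that the record is fuller than the sentence in 9.1.1 suggests. Dose delay brings in most drug-related grade 3 laboratory events. Appendix E lists transaminase and creatinine elevations and grade 4 anemia. Section 9.1.1 also requires conditions present before the first dose, and later changes in their severity, to be recorded, so a transplant cytopenia noted at baseline is followed. The word generally, the significant-worsening clause in 9.4, the optional hold in 5.7 and the Appendix E entry for other immune-related grade 3 events all let an investigator record a silent lipase value. All of this stands, and it narrows the point to the last two rows of the table. The discretionary routes do not close the gap, because they allow recording without requiring it, and practice may differ between the two sites.

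Three stronger readings are tempting and are not supported.

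- **That the stopping rules or primary endpoints undercount.** The Phase Ib endpoint starts at grade 4 non-hematologic toxicity and applies the 5.9 exceptions. The 8.6 definition names laboratory abnormalities directly. Asymptomatic grade 3 lipase counts in neither, by design. The efficacy endpoint is progression-free survival.
- **That common cytopenias or AST and ALT elevations go uncounted.** On treatment, drug-related cases mostly force a delay and are recorded.
- **That about 13% of patients would be missed.** That rate comes from another disease and pooled doses, and it mixes grades 3 and 4.

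Two further replies have some force. The documents do not say which laboratory values go onto the case report forms, so the low cost is an assumption. And dosing starts 14 to 28 days after stem cell infusion, so an unattributed worst-grade table would mix conditioning effects with drug effects; the fix needs a note saying so.

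**Conclusion.** The point holds as a minor, inexpensive improvement. Followed as written, the plan can leave asymptomatic grade 3 lipase or amylase elevation, and possibly laboratory values first found after the last dose, out of every planned safety table. The number of patients affected is unknown and may be zero; it depends on how investigators use their discretion. The lipase illustration runs from 0 to 13 points, rests on melanoma data that include a dose above the maximum tolerated dose, and is not an estimate for nivolumab 3 mg/kg with ipilimumab 1 mg/kg. The likely shift is small beside the sampling error of cohorts of 7 or 37. The effect is confined to the descriptive summary of a secondary objective.

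**What to change.** Add to 8.4.1, in words such as these:

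> Laboratory values scheduled in Appendix D will be graded by CTCAE v4.03 whether or not they were recorded as adverse events. Worst post-baseline grade and shift from Week 1 Day 1 will be tabulated by cohort. Treatment-emergent grade 3–4 values, including lipase and amylase, will be shown with exact 95% confidence intervals beside the grade 3–4 adverse event table. Early cytopenias in these tables may reflect conditioning.

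The recording, dosing and stopping rules stay as they are. The cost is one addition to the analysis text and a few tables from tests already scheduled. Section 8.7 says all study data go into SAS; the sponsor should confirm that the case report forms capture these laboratory results. The safety picture may look slightly less favourable.

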9.1.2 Serious Adverse Event Definition

A Serious Adverse Event (SAE) is any untoward medical occurrence that at any dose:

- results in death
- is life-threatening (defined as an event in which the subject was at risk of death at the time
 of the event; it does not refer to an event which hypothetically might have caused death if
 it were more severe)
- requires inpatient hospitalization or causes prolongation of existing hospitalization. The following hospitalizations are not considered SAEs:
 - a visit to the emergency room or other hospital department < 24 hours, that does not result in admission (unless considered an important medical or life-threatening event)

- o elective surgery, planned prior to signing consent
- o admissions as per protocol for a planned medical/surgical procedure
- o routine health assessment requiring admission for baseline/trending of health status (e.g., routine colonoscopy)
- Medical/surgical admission other than to remedy ill health and planned prior to entry into the study. Appropriate documentation is required in these cases
- Admission encountered for another life circumstance that carries no bearing on health status and requires no medical/surgical intervention (e.g., lack of housing, economic inadequacy, caregiver respite, family circumstances, administrative reason).
- results in persistent or significant disability/incapacity
- is a congenital anomaly/birth defect
- is an important medical event (defined as a medical event(s) that may not be immediately life-threatening or result in death or hospitalization but, based upon appropriate medical and scientific judgment, may jeopardize the subject or may require intervention [e.g., medical, surgical] to prevent one of the other serious outcomes listed in the definition above.) Examples of such events include, but are not limited to, intensive treatment in an emergency room or at home for allergic bronchospasm; blood dyscrasias or convulsions that do not result in hospitalization, or the development of drug dependency or drug abuse.)
- Potential drug induced liver injury (DILI) is also considered an important medical event.
- Suspected transmission of an infectious agent (e.g., pathogenic or nonpathogenic) via the study drug is an SAE.
- Although pregnancy, overdose, and cancer are not always serious by regulatory definition, these events must be handled as SAEs.

9.2 Pregnancy

If, following initiation of the investigational product, it is subsequently discovered that a study subject is pregnant or may have been pregnant at the time of investigational product exposure, including during at least 6 half-lives after product administration, the investigational product will be permanently discontinued in an appropriate manner (e.g., dose tapering if necessary for subject safety).

The investigator must immediately notify Worldwide Safety @BMS of this event via the Pregnancy Surveillance Form in accordance with SAE reporting procedures.

Follow-up information regarding the course of the pregnancy, including perinatal and neonatal outcome and, where applicable, offspring information must be reported on the Pregnancy Surveillance Form [provided upon request from BMS]

Any pregnancy that occurs in a female partner of a male study participant should be reported to BMS. Information on this pregnancy will be collected on the Pregnancy Surveillance Form.

9.3 Overdose

An overdose is defined as the accidental or intentional administration of any dose of a product that is considered both excessive and medically important. All occurrences of overdose must be reported as an SAE.

9.4 Other Safety Considerations

Any significant worsening noted during interim or final physical examinations, electrocardiograms, X rays, and any other potential safety assessments, whether or not these procedures are required by the protocol, should also be recorded as a nonserious or serious AE, as appropriate, and reported accordingly.

9.5 Procedures for AE and SAE Reporting

All Adverse Events and Serious Adverse Events (SAEs) that occur following the subject's first dose of therapy on Day 1 of Week 1 of combined checkpoint therapy in the study through 100 days of discontinuation of dosing or until the start of a subsequent systemic anti-cancer therapy, if earlier, must be reported to BMS Worldwide Safety, and according to local regulations. All serious adverse events (SAE) regardless of causality must be reported to the PI, (within 24 hours) and the research coordinator for notification of Hackensack University Medical Center's IRB.

The local IRB must be informed of any serious, unexpected, or alarming adverse events that occur during the approval period involving a subject within seven days of occurrence, or sooner if local guidelines apply. Any deaths of subjects require immediate (within 24 hours) reporting.

Sponsor generated reports of adverse events occurring at other investigative sites within fourteen days of receipt if the event is definitely related or possibly related to the research protocol as deemed by the sponsor lead investigator, and/or the DSMB.

Intensity for each adverse event, including any lab abnormality, will be determined by using the NCI CTCAE, version 4.03, as a guideline, wherever possible. The criteria are available online at http://evs.nci.nih.gov/ftp1/CTCAE/CTCAE 4.03 2010-06-14 QuickReference 8.5x11.pdf.

9.6 Assessment of Toxicity

Common Terminology Criteria for Adverse Events (CTCAE) will be used for the assessment and grading of all toxicities experienced by patients enrolled into this study (http://ctep.cancer.gov/forms/CTCAE Index.pdf)

If the nature of the adverse experience is listed in the CTCAE, the maximum grade will be reported.

If the adverse experience is not listed in the NCI CTCAE Common Terminology Criteria Adverse Events, report the toxicity grade using the following criteria:

- Grade 1 = Mild: an adverse experience which is easily tolerated by the patient, causing minimal discomfort and not interfering with everyday activities.
- Grade 2 = Moderate: an adverse experience which is sufficiently discomforting to interfere with normal everyday activities.
- Grade 3 = Severe: an adverse experience which is incapacitating and prevents normal everyday activities.

- Grade 4 = Life Threatening: an adverse experience which places the patient at immediate risk of death.
- Grade 5 = Death

9.7 Assessment of Causality

The local Investigator will explain each adverse experience and assess its relationship, if any, to study drug treatment. Causality will be determined by the local Investigator using the following categories: Not Related, Unlikely, Suspected (Reasonable Possibility), Probable.

- Not related: The adverse experience is definitely not related to the test drug.
- Unlikely: There are other, more likely causes and the drug is not suspected as a cause.
- Suspected (reasonable possibility): A direct cause and effect relationship between the drug and the adverse experience has not been demonstrated but there is a reasonable possibility that the experience was caused by the drug.
- Probable: There probably is a direct cause and effect relationship between the adverse experience and the study drug.

The degree of certainty with which an adverse experience is attributed to drug treatment (or alternative causes, e.g. natural history of the underlying diseases, concomitant therapy, etc.) will be determined by how well the experience can be understood in terms of one or more of the following:

Known pharmacology of the drug. Reaction of similar nature being previously observed with this drug or class of drug. The experience having often been reported in literature for similar drugs as drug related e.g. skin rashes, blood dyscrasia. The experience being related by time to drug ingestion terminating with drug withdrawal (dechallenge) or reproduced on rechallenge.

